15.1.1 Data Sets Analyzed

All analyses will be performed using a pre-/post-treatment comparison within participants. The primary safety/tolerability analysis and key secondary endpoints will be repeated in the per-protocol population, which is defined as participants having completed >80% of study drug doses and have incurred no major protocol violations. The per-protocol analyses will analyze participants according to the treatment they received.

15.2 Demographic and Baseline Characteristics

Baseline demographic and clinical characteristics of the study participants such as age, gender, race, ethnicity, height, weight, body mass index, tissue diagnosis at the time of their epilepsy surgery (when available), use of concomitant medications (AEDs) will be summarized using means and standard deviations for continuous variables, and counts and proportions for categorical variables.

15.3 Analysis of Primary Endpoint - Safety Endpoints

All reported treatment emergent SAEs and AEs will be coded using MedDRA and grouped by body system. Treatment emergent AEs are defined as AEs presenting post study treatment initiation. SAEs and AEs will be tabulated using standard coding terms sorted by body system. The incidence of AEs in each treatment arm will be tabulated by seriousness, severity, and relationship to study drug. If an AE is reported more than once during the study period for a given participant, the greatest severity and the worst-case relationship will be presented in tables.

The number of SAEs and AEs will be summarized as follows: (i) The proportion of participants with at least one (S)AE, (ii) The average number of (S)AEs per participant, and (iii) The rate of (S)AEs per participant week of follow-up. Histograms showing the frequency of the number of (S)AEs in each treatment group will be included. Rates of (S)AEs by System Organ Class (SOC) will be presented by treatment group. Poisson regression modeling will be used to derive rate ratios and 95% CIs for each SOC.

Safety lab data at each study visit and changes from baseline will be summarized by treatment group. In addition, the following clinical laboratory summaries will be presented by treatment group: (i) the incidence of clinically significant abnormalities at each study visit; and (ii) tables summarizing the frequencies of participants below, within, and above the normal reference ranges at baseline and end of study; and (iii) tables displaying baseline to end of study shifts in each laboratory value (shifts between below, within or above normal range).

The number of hospitalization events and proportion of participants hospitalized will be summarized and compared by treatment group. Poisson regression modeling will be used to derive rate ratios and 95% CIs to compare hospitalization rates between treatment groups.

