6.2 Inclusion Criteria

1. Written informed consent (and assent when applicable) obtained from participant or participant's legal representative
2. Be willing and able to adhere to the study visit schedule and other protocol requirements
3. Male or female ≥ 3 and ≤ 26 years of age at Visit 1
 - b. Because no dosing or adverse event data are currently available on the use of ABI-009 or other mTOR inhibitors in participants <3 years of age, these young children are excluded from this study.
4. Documentation of a diagnosis of medically intractable epilepsy as defined by the failure of at least 2 appropriately dosed and tolerated AEDs to eliminate all clinical seizures over a 6-month period, prior to epilepsy surgery
5. Documentation of resective epilepsy surgery following appropriate pre-surgical evaluation
6. Documentation of continued clinical seizures that persist at least 3 months following resective epilepsy surgery. In order to proceed with enrollment and study drug initiation, participants will have to have had >8 seizures in the last 30 days without 2 consecutive weeks of seizure freedom, as noted by a daily seizure diary.
7. Documentation that the participant is not a candidate for *or* refuses any additional resective epilepsy surgery
8. Participants must have adequate bone marrow function (ANC $\geq 1,000/\text{mm}^3$, platelet count of $\geq 100,000/\text{mm}^3$, and hemoglobin $\geq 9 \text{ gm/dL}$) before study drug dosing.
9. Participants must have adequate liver function (SGPT/ALT ≤ 5 times ULN and bilirubin ≤ 5 times ULN) before study drug dosing.
10. Participants must have adequate renal function, defined as: Creatinine clearance or radioisotope GFR $\geq 70\text{mL/min}/1.73 \text{ m}^2$ **or** a serum creatinine before study drug dosing based on age/gender as follows:

Age	Maximum Serum Creatinine (mg/dL)	
	Male	Female
3 to < 6 years	0.8	0.8
6 to < 10 years	1	1
10 to < 13 years	1.2	1.2
13 to < 16 years	1.5	1.4
≥ 16 years	1.7	1.4

The threshold creatinine values in this table were derived from the Schwartz formula for estimating GFR utilizing child length and stature data published by the CDC.

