9.1.5 Physical Examination

A complete or abbreviated physical examination will be performed by a licensed professional (MD, NP, RN, PA) as noted in the Schedule of Events. The abbreviated exam includes neurological, respiratory, cardiovascular, and abdominal assessments.

After screening, new abnormal physical exam findings must be documented as adverse events (AEs).

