10.3 Visit 2 – End of Baseline (Day 30 +5/-2 days)

1. Review participant diary for compliance and seizure frequency.
2. Ensure participant has had >8 seizures in the last 30 days without 2 weeks of seizure freedom to continue onto next phase.
3. Collect baseline AEs
4. Administer C-SSRS, QOLCE and NCBRF
5. Record changes to concomitant medications.
6. Perform abbreviated physical exam
7. Obtain and record vital signs. Pulse oximetry must be >93 to continue.
8. Collect blood for clinical laboratory tests (chemistry, hematology).
9. Collect urine for pregnancy test (if child-bearing potential).
 - a. If positive confirm with blood test
10. Laboratory assessments as required per the schedule of evaluations
 - a. Complete Blood Count (CBC) with differential and platelet count.
 - b. Blood chemistry assessment, including:

- i. Sodium, potassium, chloride, bicarbonate, calcium, fasting glucose, albumin,
- ii. Total protein, BUN, serum creatinine.
- iii. Total bilirubin, AST, ALT, alkaline phosphatase, uric acid, phosphorus,
- iv. Fasting serum lipid profile (total cholesterol, triglycerides, HDL and LDL)

11. Coagulation assessment, including prothrombin time, partial thromboplastin time, international normalized ratio (PT/PTT/INR).

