11 ADVERSE EXPERIENCE REPORTING AND DOCUMENTATION

11.1 Adverse Events

An AE is any untoward medical occurrence in a clinical investigation of a participant administered a pharmaceutical product and that does not necessarily have a causal relationship with the treatment. An AE is therefore any unfavorable and unintended sign (including an abnormal laboratory finding), symptom or disease temporally associated with the administration of an investigational product, whether or not related to that investigational product. An unexpected AE is one of a type not identified in nature, severity, or frequency in the current Investigator's Brochure or of greater severity or frequency than expected based on the information in the Investigator's Brochure.

The Investigator will probe, via discussion with the participant, for the occurrence of AEs during each participant visit and record the information in the site's source documents. All AEs are to be collected, from enrollment through end of the subject's study participation, and recorded in the participant CRF. Attribution will be unrelated, unlikely, possible, probably, or definite.

Taking into account the targeted population and the secondary endpoints of the study, Grade 1 and 2 seizures as defined by the National Cancer Institute's Common Terminology Criteria for Adverse Events (CTCAE) v5 will not be tracked as adverse events and will not be included in the baseline patient assessment.

AE Severity

The CTCAE v5 should be used to assess and grade AE severity, including laboratory abnormalities. If the experience is not covered in the modified criteria, the guidelines shown in Table 3 below should be used to grade severity. It should be pointed out that the term "severe" is a measure of intensity and that a severe AE is not necessarily serious.

Table 7. AE Severity Grading

Severity (Toxicity Grade)	Description
Mild (1)	Mild; asymptomatic or mild symptoms; clinical or diagnostic observations only; intervention not indicated
Moderate (2)	Moderate; minimal, local or noninvasive intervention indicated; limiting age-appropriate Instrumental activities of daily living (e.g., preparing meals, using the telephone, managing money)
Severe (3)	Severe or medically significant but not immediately life-threatening; hospitalization or prolongation of hospitalization indicated; disabling; limiting self-care activities of daily living (e.g., bathing, dressing, feeding self, using toilet, taking medications)

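### The treatment-emergent AE definition has no clause for worsening, so a baseline condition that rises in grade on ABI-009 may be missed in the AE tables

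*Combined protocol and SAP*

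**What the plan says.** Section 15.3 opens the primary safety analysis with "All reported treatment emergent SAEs and AEs will be coded using MedDRA and grouped by body system", and then gives the definition: "Treatment emergent AEs are defined as AEs presenting post study treatment initiation". It adds a rule for repeats: "If an AE is reported more than once during the study period for a given participant, the greatest severity and the worst-case relationship" are what the tables show. Other sentences in the section, on tabulating and counting SAEs and AEs, do not carry the treatment-emergent qualifier.

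Events can start before dosing. Section 11.1 says "All AEs are to be collected, from enrollment through end of the" participant's time on study. Section 10.3 lists "Collect baseline AEs" among the Visit 2 tasks, at the end of a baseline period that Section 15.1 sets at Days 0-30. Section 9.1.14 lists what the CRF holds for each AE: start and end dates, grade, seriousness, outcome, treatment and relation to drug. Section 9.1.5 obliges staff to record only new abnormal examination findings as AEs.

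Laboratory data have their own summaries in Section 15.3, none tied to treatment-emergent status: values and changes from baseline at each visit, the incidence of clinically significant abnormalities at each visit, and range and shift tables from baseline to end of study. Section 5.1 makes clinically significant abnormal laboratory values part of the primary safety endpoint alongside AEs.

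**The concern.** AE incidence is a primary endpoint, and Section 15.1.1 frames all analyses as within-participant comparisons of before and after treatment. Such a comparison needs a rule for an event that spans the first infusion, and no section supplies one. Section 15.3 goes by when an event presents. Section 9.1.14 stores one start date and does not ask when a grade changed. An event that started in baseline and became more severe on drug would ordinarily be dated to baseline and fall outside the coded treatment-emergent tables.

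If that happens, the error runs in one direction: reported incidence is too low. Non-laboratory events are the most exposed, because they have no second set of summaries. Section 2.1 names rash, fatigue and infections, among others, as common reactions to this drug class. A participant may have a mild form of any of these in the baseline month. Two analysts could also build different primary tables from the same data, depending on how each reads the definition.

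**Working it through.** The main check is a comparison of sections. The only arithmetic is an illustration of size at the end.

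**1. A non-laboratory event that spans the first infusion (hypothetical).** Fatigue starts on Day 10 at grade 1 and becomes grade 2 after the second infusion. Visit 2 is Day 30 (+5/-2 days) and may also be the first dosing visit, so dosing starts no earlier than Day 28.

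- One CRF record under Section 9.1.14: start Day 10, grade 2.
- Read by onset date: Day 10 is before Day 28, so the event is not treatment-emergent.
- Read with the worsening as a separate event: it presents after dosing, so it is treatment-emergent.
- The repeat rule in Section 15.3 does not decide between these. It picks the highest grade over the whole study period without separating the time before and after the first infusion, and with a single record it is not triggered.

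**2. Laboratory worsening within one category.**

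| Input | Value | Source |
|---|---|---|
| Lowest ANC at entry | 1,000/mm3 = 1.0 x10^9/L | Section 6.2, item 8 |
| Neutrophils, grade 1 or better | >=1.5 x10^9/L | Table 4 |
| Neutrophils, grade 4 | <0.5 x10^9/L | Table 4 |
| Highest ALT and bilirubin at entry | "SGPT/ALT ≤ 5 times ULN and bilirubin ≤ 5 times ULN" | Section 6.2, item 9 |

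- ANC 1.1 at baseline: 1.1 >= 1.0, so eligible; 1.1 < 1.5, so already abnormal by Table 4. A fall to 0.4 is grade 4, since 0.4 < 0.5. If 0.4 is the end-of-study value, the shift table shows below to below: no shift. This assumes that the laboratory's lower normal limit lies above 1.1; the documents do not give it.
- ALT 2 x ULN at baseline is eligible. A rise to 8 x ULN that persists shows above to above: no shift.

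The ANC change, 0.4 - 1.1 = -0.7 x10^9/L, does enter the change-from-baseline summary. In a cohort of 3 with the other two unchanged, the mean change is -0.7/3 = -0.23.

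**3. Transient laboratory worsening.** In Appendix 1 the blood count is drawn at every dosing visit and at Visit 6, and then only conditionally at Visit 7. A value that is normal at baseline, low at Visit 4 or 5 and normal at the last draw shows within to within. The by-visit summaries would show it; the shift table would not.

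**4. What does not depend on the definition.** Section 8.5 defines a DLT by grade, attribution and time window. Section 14 has the DSMB review all AEs, at minimum before each escalation cohort and before the MTD expansion.

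**5. Illustrative size.** The MTD group holds 3 or 6 participants plus 6 in expansion, so 9 or 12. One omitted participant lowers incidence by 1/9 = 11.1 or 1/12 = 8.3 percentage points. Exact 95% intervals for n = 9:

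- 0/9: lower 0; upper 1 - 0.025^(1/9) = 34%.
- 1/9: lower 1 - 0.975^(1/9) = 0.3%; upper solves (1-p)^9 + 9p(1-p)^8 = 0.025, giving 48%.

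These figures assume exactly one omission, a frequency that the documents do not give.

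**The case against.** The strongest reply is that the plan is silent on worsening and does not exclude it. Section 15.3 says *presenting*, without *first*. Section 11.1 defines an AE broadly, as "any unfavorable and unintended sign (including an abnormal laboratory finding), symptom or disease temporally associated with the administration" of an investigational product, so an investigator could record a worsening as a new, post-dose AE. Section 8.7.4 tells participants to report new or worsening respiratory symptoms. The duty in Section 9.1.5 to record new findings covers physical examination only. On one reading, the unqualified tabulation sentences and the repeat rule would show a worsened baseline event at its highest grade. All of this stands, and it means that omission is a risk and not a stated rule. It does not settle the matter, because none of these sentences tells the analyst how to classify an event that began before dosing.

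A reader might infer three stronger things. The first is that worsening laboratory values vanish from the primary safety tables. They do not: changes from baseline and clinically significant abnormalities are summarized at every visit. The ANC fall to 0.4 could also be recorded as a post-dose AE, and Table 4 would trigger a recorded dosing action. The second is that the MTD is compromised. It is not, since DLTs are assessed without reference to treatment-emergent status. The third is that a known share of toxicity is being lost. Nothing in the documents gives such a share.

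Finally, Section 15.1 promises a detailed SAP that may modify this plan. That could repair the definition, but Section 15.1 makes no commitment on this point. A later SAP may also be unable to recover a date of worsening that the CRF never asked for.

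**Conclusion.** The point holds in limited form. The definition in Section 15.3 lacks a worsening clause, and the CRF content in Section 9.1.14 does not supply the date needed to apply one. Non-laboratory events that begin in baseline and rise in grade on drug may therefore be missed, and any resulting bias in AE incidence is downward. For laboratory data the weakness is narrower: the shift tables cannot show worsening within a category or a transient change, although the by-visit summaries capture part of it. Dose escalation, the MTD and DSMB review are untouched.

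The size is unknown. The shift of 8 to 11 percentage points per omitted participant, and 0/9 against 1/9, only show how sensitive so small a group is. The conclusion assumes that a worsened event stays on its existing CRF line; if sites open a new line unprompted, the loss is smaller. Because a primary endpoint is affected and the repair is cheap, the change should be made, but it is not a reason to stop the trial from proceeding.

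**What to change.** 1. In Section 15.3, define a treatment-emergent AE as one with onset on or after the first infusion, or one present before it whose CTCAE grade afterwards exceeds its worst grade in the baseline period. State which of the section's AE counts and tables are restricted to such events.
2. In the CRF instructions for Section 9.1.14, require a new AE line, with its own start date and grade, on the date an existing event worsens.
3. Add laboratory shift tables from baseline grade to worst post-baseline CTCAE grade, using all post-dose draws.

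The cost is one sentence, one CRF instruction and one extra table. No visit, sample or treatment rule changes. Reported incidence may become slightly less favourable. The CRF instruction should be in place before events accrue, because dates of worsening may not be recoverable later.

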ENDPOINTS	
Seizure frequency Percentage reduction in seizure frequency Median percentage reduction in seizure frequency Response rate Frequency of seizure-free days Seizure-free rate Rapamycin blood level–response relationship
 
Other:
 
Quality of life and behavioral index Determine weekly whole blood rapamycin trough levels for three consecutive weeks

STATISTICS Primary Analysis Plan	
Analysis of Primary Endpoints
 
The number of SAEs and AEs will be summarized for each dosing group as follows: (i) The proportion of participants with at least one (S)AE, (ii) The average number of (S)AEs per participant, and (iii) The rate of (S)AEs per participant week of follow-up. Histograms showing the frequency of the number of (S)AEs in each dosing group will be included. Rates of (S)AEs by System Organ Class (SOC) will be presented by treatment group. Poisson regression modeling for count data will be used to derive rate ratios and 95% CIs for each SOC.
 
Safety lab data at each study visit and changes from baseline will be summarized by dosing group. In addition, the following clinical laboratory summaries will be presented by dosing group: (i) the incidence of clinically significant abnormalities at each study visit; and (ii) tables summarizing the frequencies of participants below, within, and above the normal reference ranges at baseline and end of study; and (iii) tables displaying baseline to end of study shifts in each laboratory value (shifts between below, within or above normal range).
 
The number of hospitalization events and proportion of participants hospitalized from baseline to final day of study will be summarized and compared by treatment group. Poisson regression modeling will be used to derive rate ratios and 95% CIs.
 
Study compliance will be assessed via compliance with scheduled weekly infusions.
 
Analysis of Secondary Endpoints
 
Efficacy is defined as the change in seizure frequency between baseline and follow-up, expressed as percentage reduction in seizure rate (reduction in seizure frequency from baseline, calculated as (Baseline frequency [seizures/week] – frequency at follow-up

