15 STATISTICAL METHODS AND CONSIDERATIONS

15.1 General Considerations

Prior to the analysis of the final study data, a detailed Statistical Analysis Plan (SAP) will be written, describing all analyses that will be performed. The SAP will contain any modifications to the analysis plan described below.

For the purposes of analyses, baseline period will be defined as Days 0-30. Except where otherwise noted, comparisons of continuous variables between pre and post treatment periods will utilize t-tests or linear regression, test of proportions and analysis of count data using Poisson regression. Except where otherwise noted, all tests will be two-sided and statistical significance will be determined at the 0.05 level. Missing data methods for the primary and key secondary endpoints will be described in the SAP. No adjustment for multiple comparisons will be made.

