15.6 Sample Size

This is intended to be small phase 1 study of an orphan disease focusing on safety and tolerability as primary endpoints. We anticipate recruiting up to 18 patients for studying an orphan disease, taking into account recruitment feasibility and the 3+3 dose escalation paradigm with an MTD cohort expansion.

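### Plain Poisson regression for adverse-event and hospitalization rate ratios allows for no extra-Poisson variation, so intervals for frequent events will be too narrow if counts vary more than Poisson

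*Combined protocol and SAP*

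**What the plan says.** Section 15.3 sets the method for adverse-event (AE) rates by SOC: "Poisson regression modeling will be used to derive rate ratios and 95% CIs for each SOC". The synopsis says the same: "Poisson regression modeling for count data will be used to derive rate ratios and 95% CIs for each SOC". For hospitalizations, 15.3 adds: "Poisson regression modeling will be used to derive rate ratios and 95% CIs to compare hospitalization rates between treatment groups".

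Section 15.1 lists default methods for comparing the periods before and after treatment, including "test of proportions and analysis of count data using Poisson regression". It sets the error rate: "all tests will be two-sided and statistical significance will be determined at the 0.05 level".

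Section 15.1.1 states: "All analyses will be performed using a pre-/post-treatment comparison within participants". Section 15.3, however, compares treatment groups and analyses only events that begin after treatment starts, so the contrast behind each SOC rate ratio is not fully defined.

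No section mentions overdispersion, a scale parameter, a negative binomial model, robust or clustered variance, a participant effect or an exposure offset. Section 15.1 defers detail to a later SAP: "The SAP will contain any modifications to the analysis plan described below". It says explicitly that missing-data methods will be given there, but makes no such promise about dispersion.

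**The concern.** A Poisson model takes the variance of a count to equal its mean, as if every event were independent. The standard error of a log rate ratio then depends only on the total events in each group. Twelve events in a group of three give the same interval whether they fall 4, 4 and 4 or 10, 1 and 1, so one participant with many events can make a dose-group contrast look precise.

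The documents give reasons to expect participants to differ:
- Section 15.3 provides for an AE that the same participant reports more than once, and for histograms of AE counts.
- Section 8.6.1 places users of CYP3A4 inducers in the same dose groups without adjustment.
- Section 1.13 reports trough levels of 4.3 to 9.1 ng/ml at one dose, about a 2-fold range (9.1/4.3 = 2.1), from a study in which 3 participants supplied levels.

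At stake is how the primary safety tables are read. An apparent dose-related difference in a common SOC could be reported as significant when it reflects one or two participants.

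**Working it through.** **Inputs from the documents.** Two-sided alpha is 0.05 (15.1). Dose groups have 3 participants, or 6 after a DLT, and the MTD group gains an estimated 6 (4.1), giving 9 or 12. The total is at most 18 (15.6). Baseline is 30 days (15.1). The post-treatment period is taken as 21 dosing days plus 90 days of visits, 111 in all.

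**Assumed, because the documents give no value.** Mean events per participant, mu, and between-participant variance of the rate relative to its squared mean, k (gamma). Variance/mean is then phi = 1 + k × mu.

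**Step 1: the plan's own figure.** For large counts, the true error rate of the Poisson Wald test is 2 × (1 − Φ(1.96/√phi)). At phi = 1 this is 0.050, so the plan's 0.05 is reproduced when counts are truly Poisson.

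**Step 2: the same formula with extra variation.**

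| phi | True error rate | Coverage of the 95% CI |
|---|---|---|
| 1.5 | 0.110 | 89% |
| 2 | 0.166 | 83% |
| 3 | 0.258 | 74% |
| 5 | 0.381 | 62% |

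At mu = 4, k of 0.25 to 1 gives phi = 1 + 0.25 × 4 = 2 up to 1 + 1 × 4 = 5, hence 0.17 to 0.38.

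**Step 3: simulation at the trial's group sizes.** True rate ratio 1; groups 3 v 3, 3 v 9, 3 v 12 and 6 v 12; plain Poisson Wald test.

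| Events per participant | k | Error rate |
|---|---|---|
| 0.5 | 0 to 1 | 0.00 to 0.06 |
| 1 | 0 to 1 | 0.00 to 0.11 |
| 3 | 0.25 to 1 | 0.11 to 0.31 |
| 4 | 0.25 to 1 | 0.15 to 0.38 |
| 10 | 0.25 to 1 | 0.28 to 0.55 |

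More events make the error worse, so this is a different problem from sparse or zero cells.

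**Step 4: one interval.** Take 3 v 12 at 4 events each: 3 × 4 = 12 and 12 × 4 = 48 events, observed rate ratio 1. The Poisson SE of the log ratio is √(1/12 + 1/48) = 0.323, giving a CI of exp(±1.96 × 0.323) = 0.53 to 1.88. With phi = 3 and t on 15 − 2 = 13 df (2.16), the half-width is 2.16 × √3 × 0.323 = 1.21 and the CI is 0.30 to 3.34, about 1.9 times as wide on the log scale.

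**Step 5: the remedy between groups.** Pearson-scaled standard errors (scale not below 1) with t quantiles, k of 0.25 to 1, give 0.03 to 0.05 for 3 v 9, 3 v 12 and 6 v 12. Log-scale intervals are about 1.4 to 2.0 times wider at 3 events per participant and 1.9 to 3.3 times at 10. For 3 v 3 the error rate is only 0.003 to 0.03, which is very conservative.

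**Step 6: pre/post counts, 30 v 111 days.** With stable participant differences only (n = 18, k = 0.5 or 1), plain Poisson stays at 0.046 to 0.051, because a stable participant effect cancels. With participant-by-period variance of 0.1 to 0.5 (n = 9 or 18, k = 0.5, 3 or 10 events per 30 days), it rises to 0.12 to 0.57. Participant-clustered variance with t quantiles gives 0.06 to 0.09.

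**The case against.** The strongest reply is that the size rests on assumed dispersion. The documents state none, and at phi = 1 the planned intervals are correct. That stands: the intervals are too narrow only if counts vary more than Poisson.

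Second, the model is applied SOC by SOC, over three doses, and section 11.1 does not track grade 1 and 2 seizures as AEs. Many SOCs may have about one event per participant or fewer, where the plain test is conservative or only modestly inflated. This also stands; the same holds for hospitalizations if they are rare.

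Third, 15.3 also reports the proportion of participants with at least one event and histograms of event counts, which would show one person driving a total. That helps a careful reader but does not correct the intervals.

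Fourth, the later SAP could add an allowance. It could, but the present text neither makes nor promises one.

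A reader might also infer that the 15.1 default would put seizure counts through a Poisson test, with a large excess of false positives. The documents do not support that. The default yields wherever another method is named. Section 15.5 gives the t-test and ANOVA as examples for the seizure endpoints, and the synopsis gives tests of proportions and time-to-event methods. The main endpoints, such as percentage reduction and response, are summarized per participant. The lists are examples only, so a sentence closing the gap is worthwhile, but no Poisson seizure analysis is planned.

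**Conclusion.** The concern holds in conditional form. The plan names plain Poisson regression for between-dose-group AE and hospitalization rate ratios, and as the default for pre/post counts, with no provision for extra-Poisson variation. If between-participant variance is 0.25 to 1, error rates for frequent-event SOCs are about 0.15 to 0.38 at 4 events per participant and 0.28 to 0.55 at 10, instead of 0.05. At 1 event or fewer they are 0.00 to 0.11. These ranges depend on the assumed variance and event rates. The exposure and inducer passages make such variation plausible but do not measure it.

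The two comparisons must be kept apart. Between dose groups, differences between participants matter. In within-participant pre/post comparisons, only participant-by-period variation does.

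Nor should a reader infer that dose escalation is at risk. Section 4.1 bases escalation and the MTD on DLT counts, and section 14 adds board review; neither uses these models. The effect is on the reported safety comparisons, and it should be corrected before the final analysis.

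**What to change.** In 15.3, the synopsis and the SAP:
- State the contrast for each SOC and hospitalization rate ratio, and include a log person-time offset.
- Use Pearson-scaled (quasi-Poisson) standard errors, with the scale not allowed below 1, and t quantiles on participants minus groups degrees of freedom.
- Report 3 v 3 comparisons descriptively, because the scaled interval is very conservative there.

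In 15.1:
- Replace plain Poisson for any pre/post count with a participant-level paired or participant-clustered analysis that can handle zero counts. One log rate ratio per participant will not do by itself, since it is undefined for a participant with no events in a period.
- State that seizure counts will not be analysed by plain Poisson regression.

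The cost is a few sentences, a few lines of code and wider intervals. No visit, dose or data collection changes.
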